7.1 Test program evaluation

①Demographic data: age, sex, and ethnic group.

⁽²⁾History: ask for or collect current and past medical history based on existing medical records.

③Medication history: before taking the test, take the prescription or over-the-counter drugs, and record the generic name, daily total dose, usage and cause of use of the drug.
④The diagnosis of disease was confirmed by CT or MRI, and the amount of cerebral hemorrhage was calculated at the later stage (after the onset of the disease, the examination was not repeated).

⁽⁵⁾Physical examination: vital signs include body temperature (Ye Wen), respiration, heart rate, and blood pressure.

⁽⁶⁾Assessment of biological specimen collection and laboratory: collected blood and urine of Hematology, serum biochemistry, pregnancy test and laboratory examination, biological specimens from all participating units of the laboratory is responsible for collecting, processing, preservation and detection. Prior to the signing of the test drug, the clinical trial participant shall provide the bid with the normal reference range of the laboratory indicators. If there is any change during the test period, the applicant shall be promptly informed of the bid.

⑦Scale evaluation: mRS score.

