7.2 Test procedure

Subject to any test procedure, the subjects, legal agents and / or subjects must have read and signed an informed consent letter approved by the ethics committee. The test

procedure shall be carried out within the prescribed time window of the visit, as detailed in the test flow chart.

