7.5.3 Medication and treatment are permitted

(1) The other combined diseases without affecting the curative effect and safety evaluation, can be symptomatic medication, but it must be the case report form to record the medicine general or other treatment, dosage, reason, use frequency and time etc, so as to summarize, analyze and report.

⁽²⁾The follow-up period can use cognitive rehabilitation methods, including occupational therapy, implicit memory rehabilitation, errorless learning, cognitive neuropsychological rehabilitation, rehabilitation and computer assisted cognitive rehabilitation, virtual remote control via the Internet, and the electromagnetic stimulation, should be recorded in detail in CRF.

⁽³⁾The combination drugs used for adverse events during the trial should be recorded in CRF.

8 Therapeutic evaluation standard

Main outcome measures: the amount of intracerebral hemorrhage (0d, 1D, 3D, 7D) at each time after the onset of disease.

Main outcome measures: (1) the amount of the time changes in blood coagulation, platelet levels and GCS scores after the onset (0d, 1D, 3D, 7D); (2) days in ICU; (3) the total hospitalization days; (4) complications including neurological complications, complications, blood coagulation circulatory complications after cerebral hemorrhage; (5) 1m and 6m mRS score.

9 Safety evaluation

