Statistical analysis plan

1. Statistical software

Using STATA version 12.0 statistical software.

2. Special data processing

(1) Missing data: When a certain important data due to loss, miss follow-up, examination is happen, the LOCF method will be adopted to carry out the data and the secondary index will not be transferred.

(2) Outlier data: According to statistical and medical analysis, determine these data will be included or not. Sensitivity analysis was conducted for the outliers of the main targets, including two results consistent with those who did not outliers.

3. Selection of inspection level α and power of test β

(1) Difference test: With $\alpha = 0.05$ as the test standard, two-sided test was adopted, and the statistical methods, statistics and specific P values were given. $P \leq 0.05$ was considered statistically significant.

(2) Superiority test: Based on a power of 80% ($\beta = 0.2$), $\alpha = 0.025$ was conducted for the one-sided test. The difference between the groups and the 95% confidence interval of the mRS score difference to the baseline values after treatment in the experimental group and the placebo group was calculated by the least square method. If the 95% confidence interval between the two groups was greater than 0, the experimental group can be thought to be superior to the placebo group, otherwise not.

4. Statistical expression

(1) The statistical report mainly expressed in form, which was self-evident. It had the title, the heading and the number of cases, the necessary remarks and the text of statistical results and the description of data results.

(2) Descriptive statistics: The measurement data is described by mean number, standard deviation, maximum value, minimum value, 95% confidence interval, median, Q1 and Q3. The enumeration data is described by frequency (constituent

ratio), and corresponding statistics and P value are calculated.

(3) Inferential statistics: Measurement data were compared between groups by analysis of variance or K-W rank-sum test according to the distribution pattern. Enumeration data were compared between groups by R*C Chi-squared test and Fisher exact test. The ranked data was tested by CMH. The main/important therapeutic effect index will use the baseline for the covariant, considering center, operation or not after injury for analysis of covariance.

5. Specific statistical analysis content

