(1) Analysis of program implementation: a list was adopted to summarize the entry and completion of all and each central cases, and tabulate details and the data collation of those cases which are not meet the inclusion criteria, fall off, low compliance, against therapy and drug combination, interview time beyond window.

(2) Analysis the patient compliance and the drug combination during the trail.

(3) Condition of each analysis data set: Based on the analysis of the implementation of the program, determining the data imputation of each deviated test programme case. Summarize the cases of each analysis data sets, such as per-protocol set (PPS), full analysis set (FAS), safety set (SS).

(4) Baseline equalization analysis: Compare the baseline data of demographic data, vital signs and medical history related features.

(5) Analysis of curative effect index :

1) Compare the changes of mRS score to the baseline after using the drug in 2 days, followed up with 1 month and 6 months in the two groups. The main/important therapeutic effect index will use the baseline for the covariant, considering center, operation or not after injury for analysis of covariance. The covariance analysis was performed on the change of mRS score at baseline after 6 months of follow-up. The difference between the groups and the 95% confidence interval of the mRS score difference to the baseline values after treatment in the experimental group and the placebo group was calculated by the least square method. If the 95% confidence interval between the two groups was greater than 0, the experimental group can be

thought to be superior to the placebo group, otherwise not.

2) Compare the changes of cerebral hemorrhage amount to the baseline in the two groups.

3) Compare the changes of coagulation function, platelet level and GCS score to the baseline in the two groups.

4) Compare the number of days stayed in the ICU and the hospital in the two groups.

(6) Safety analysis:

Compare the incidence and classification rate of complications, adverse events and adverse reactions during the test in the two groups, and list the details of each adverse event, such as the detailed occurrence, outcome and the relationship with drugs.

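### Day-1 haematoma volume is listed as a main outcome, but the CT schedule is unclear, and if volume counts as a main index, LOCF would set every missed day-1 change to exactly 0 mL

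*Protocol*

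**What the plan says.** - **Outcome.** Protocol section 8 opens with "Main outcome measures: the amount of intracerebral hemorrhage (0d, 1D, 3D, 7D) at each time after the onset of disease". A second list follows under the same label, covering coagulation, platelets, GCS, length of stay, complications and mRS. The section therefore does not mark cleanly which outcomes are secondary.
- **Imaging at diagnosis.** Section 7.1 item 4 has the diagnosis confirmed by CT or MRI and adds that "the amount of cerebral hemorrhage was calculated at the later stage (after the onset of the disease, the examination was not repeated".
- **Visit timing.** Section 7.2 refers to the chart for timing: "procedure shall be carried out within the prescribed time window of the visit, as detailed in the test flow chart".
- **Flow chart (7.5).** As extracted, the CT volume row is ticked at D0, at a column whose heading came out as 50 (presumably D3), at D7, and at discharge or death. The D1 cell is empty.
- **Missing data.** For data it regards as important, SAP 2(1) says "the LOCF method will be adopted to carry out the data and the secondary index will not be transferred".
- **Analysis.** SAP 5(5) item 2 reads, in full, "Compare the changes of cerebral hemorrhage amount to the baseline in the two groups". It names no time point. The covariance analysis in item 1 is tied to another endpoint: "The covariance analysis was performed on the change of mRS score at baseline after 6 months of follow-up".

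**The concern.** The stated purpose of the trial is to see whether vitamin K1 prevents the haemorrhage from enlarging. Day 1 is the first post-baseline volume in section 8, and it falls during the two-day treatment period. The protocol does not say consistently whether a scan is taken then. In a multicentre trial, centres could follow different passages and collect different scans, and a day-1 scan that was not taken cannot be recovered.

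The missing-data rule adds to this. Carrying the last observation forward to the first post-baseline time point means carrying baseline forward. The imputed value then asserts that the haematoma did not change, which is the very question the outcome is meant to answer.

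**Working it through.** The documents give no sample size, effect size, standard deviation or expected missing share for volume, so there is no figure of the plan's own to reproduce. The check compares the passages and then works through the LOCF arithmetic.

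**1. Is a D1 scan scheduled?**
- Section 8: yes, at 0d, 1D, 3D and 7D.
- Flow chart as extracted: D0 ticked, D1 blank, presumed D3 ticked, D7 ticked, discharge or death ticked.
- Section 7.1 item 4: unclear. Read literally it allows no later scan. Read in context it may concern only the diagnostic scan.

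**2. What LOCF does to one patient with no D1 volume.** The only earlier value is V(D0), so V(D1) is set to V(D0). The day-1 change is V(D0) - V(D0) = 0 mL, whatever the haematoma did.

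**3. What it does to the group difference.** Let the true mean day-1 growth be g_C in control and g_T in the test arm, with missing shares m_C and m_T unrelated to growth. The expected difference after LOCF is

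(1 - m_C) g_C - (1 - m_T) g_T.

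If m_C = m_T = m, this is (1 - m)(g_C - g_T).

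**4. Illustration.** Assumed values, not from the documents: g_C = 5 mL, g_T = 3 mL, SD 8 mL, so the true difference is 2 mL.
- m = 10%: 0.90 x 2 = 1.8 mL (simulated 1.74)
- m = 25%: 0.75 x 2 = 1.5 mL (simulated 1.47)
- m = 50%: 0.50 x 2 = 1.0 mL (simulated 0.95)

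**5. The spread shrinks too.** The variance after LOCF is (1 - m) x SD² + m(1 - m) x g². At m = 50% this is 32 + 6.25 = 38.25 in control and 32 + 2.25 = 34.25 in the test arm, a pooled SD of √36.25 = 6.02 mL. The standardised difference goes from 2/8 = 0.25 to 1.0/6.02 = 0.166, about 0.66 of its true value. Analysing only the observed half would scale the test statistic by √0.5 = 0.71. In this example the main harm is therefore to the estimate and its confidence interval. The loss of power beyond that from having fewer scans is small.

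**6. If missingness differs by arm.** With the same growth values:
- m_C = 50%, m_T = 25%: 0.50 x 5 - 0.75 x 3 = 2.5 - 2.25 = 0.25 mL
- m_C = 25%, m_T = 50%: 0.75 x 5 - 0.50 x 3 = 3.75 - 1.5 = 2.25 mL

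The distortion can then go either way. If scans are taken mainly in patients who deteriorate, the (1 - m) factor does not hold either.

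**The case against.** Three stronger readings are tempting, and the documents do not support them.

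- **The flow chart schedules no D1 scan, so every day-1 change becomes zero.** The chart has visibly lost marks. A heading is misread, and stray characters stand where ticks would be. GCS shows no tick before month 1, although section 8 asks for it at 0d, 1D, 3D and 7D. Vital signs show none at D1 or D3. The blank CT cell may be another lost tick. In its favour, the D1 column does carry a tick in the drugs-and-dosages row, and the blood-routine row shows the same pattern as CT. That justifies checking the original but does not establish a plan error.
- **Section 7.1 bans repeat CT.** The remark stands in the item on confirming the diagnosis, and may mean only that a scan already done after onset need not be redone. As a ban it would also contradict the chart's later CT ticks, so it is not specific evidence against a D1 scan. It does mention calculating the volume, which is the outcome, so it still needs clarifying.
- **LOCF will be applied to day-1 volume.** The SAP exempts the secondary index, ties its 6-month covariance analysis and superiority rule to mRS, and names no day-1 volume analysis. If the sponsor treats volume as secondary, nothing is carried forward. A scan that was never scheduled is also not obviously missing data in the SAP's sense.

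It is also fair to say that with one infusion a day for two days, the course may be incomplete at D1. D3 is the first listed reading after it, and the D3 and D7 readings remain.

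What survives does not depend on the chart. Section 8 calls volume a main outcome, and SAP 2(1) exempts only secondary indices. On that reading, any missed D1 scan, scheduled or not, can be filled only from baseline.

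**Conclusion.** The point holds conditionally. Section 7.1 item 4, the flow chart and section 8 do not give one clear CT schedule, and the D1 cell has to be verified in the original. If volume is handled as the main outcome that section 8 calls it, LOCF turns each missed day-1 change into exactly 0 mL. The day-1 group difference then shrinks to (1 - m) of its true value (0.75 at 25% missing, 0.50 at 50%), provided missingness is equal by arm and unrelated to volume change. The values of m are illustrative, since the documents give none.

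A reader might infer that the main outcome is lost or the trial's conclusion compromised. That does not follow. The effect is limited to early volume comparisons. It does not reach the mRS analysis, and there is no sample-size figure for it to affect. It is a correctable weakness in wording and missing-data handling.

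**What to change.** 1. **One schedule.** Check the D1 CT cell in the original flow chart. Then reconcile section 7.1 item 4, the chart and section 8 so that all three give the same CT time points. Which time points to keep is the sponsor's choice.
2. **Missing-data rule.** State in SAP 2(1) that a baseline volume is never carried forward as a post-baseline volume. State also whether volume is a main or a secondary index.
3. **Analysis.** In SAP 5(5) item 2, name the volume time points and analyse the observed volumes with a likelihood-based repeated-measures model adjusted for baseline volume. Such a model relies on data being missing at random given the observed volumes, a weaker assumption than no change since baseline.

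The cost is wording in both documents and a small amount of extra analysis work.

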9.1 Definition

Adverse events (Adverse, Event, AE): refers to the patient or clinical trial subjects after receiving a drug adverse medical events, but not necessarily have a causal relationship with the treatment.

Serious adverse events (Serious Adverse, Event, SAE): the need for hospitalization, prolonged hospitalization, disability, affecting work ability, endanger life or death, resulting in congenital malformation occurred during the clinical trial.

Important adverse events are any adverse events or laboratory abnormalities that result from the use of targeted medical measures (such as discontinuation, dosage reduction, and / or symptomatic treatment) other than SAE.

Adverse drug reactions (ADR): adverse reactions that occur when prescribed drugs are applied at prescribed doses, not as desired, but are causally related to the use of the drug. In a clinical trial of a new drug or a new drug, when the dose of treatment has not yet been determined, all harmful reactions that are not expected to cause a causal relationship with the use of the drug should be considered adverse drug reactions.

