9.3 Handling and recording of adverse events

9.3.1 Treatment for adverse events

Inpatient

If the subject has adverse events during hospitalization, follow the following procedures:

Found adverse events in subjects, tube bed doctor or the doctor on duty shall promptly inform researchers, if necessary, can be the first symptomatic treatment, the degree of correlation between classification by research physician preliminary assessment of adverse events and drug test, and give further advice:

- ① General adverse events: can closely observe the outcome of the event or the corresponding symptomatic treatment;
- ② Important adverse events: physicians should promptly inform major researchers, and pause treatment, adjust drug dosage and targeted treatment according to the subjects' condition;
- ③ Serious adverse events: follow "9.4" for processing and reporting.
- ④ According to the patient's treatment, if the subject's injury exceeds the capacity of the research department, the relevant department should be invited to consult and assist in the treatment.

Outpatient

The adverse events that the subjects after the study, physicians should ask detailed subjects at the time of the symptoms and signs and place, the necessary explanation and

guidance on the subjects, and the degree of correlation of adverse events and give preliminary evaluation; as the subjects in the local medical institutions, contact by telephone and reception the doctor, check again the degree of adverse events and give treatment advice:

 General adverse events: initial visit to local hospital and notification of outcome of close observation;

⁽²⁾ Important adverse events: recommend returning to the hospital for treatment or to the local hospital for treatment, and timely notification of the main researchers, such as limited local hospitals, doctors should be sent to the treatment. An emergency envelope is also provided for emergency blind use (if applicable). According to the plan request, adopts the pause treatment, adjusts the medicine dosage and the symptomatic treatment and so on.

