9.4.3 Hospitalization

Adverse events leading to hospitalization or prolonged hospitalization in clinical trials should be considered as serious adverse events. Any first hospitalized (even shorter than 24 hours). Is according to comply with this standard..

Hospitalization does not include the following circumstances:

• Rehabilitation facility

- Nursing home
- Routine routine emergency room admission
- O day surgery (e.g. outpatient / day / ambulatory surgery)

Hospitalization or prolonged hospital stays unrelated to worsening adverse events are not, in themselves, serious adverse events, for example:

- Because of the original disease, there is no new adverse event, and there is no exacerbation of the original disease.
- Management for reasons of hospitalization (e.g. routine annual examination).
- Clinical setting during the clinical trial (for example, according to the requirements of the test program).
- elective hospitalization with adverse events worsening (e.g., elective cosmetic surgery).
- scheduled treatment or surgery should be performed throughout the trial program.
- admission only because of blood use.

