9.5 Grading of adverse events

Mild: mild symptoms can be tolerated, does not affect activities of daily living, symptoms are transient, in the continuing use of drugs during their own relief, without treatment.

Moderate: the symptoms are obvious, affecting the daily activities of the subjects, the symptoms for a long time, can be relieved or symptomatic relief after treatment. It may interfere with the use of investigational drugs, such as reducing drug dosages or stopping medications.

Severe: the subjects suffered from impaired body function, lost normal work and living ability, and had a long duration of symptoms. They had to be stopped and properly treated before they could be relieved

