9.6 Adverse events and test drug evaluation

According to the sequence between the occurrences of adverse drug evens and usage of drugs, the type of drug reaction after drug withdrawal reaction is reduced, will disappear or reappear, causality assessment of adverse events related to study drug is certainly relevant, probably, may be related, and certainly can not. The first three were considered to be relevant to the study of the drug, which was evaluated as untoward effect of drug.(ADR).

Adverse events associated with the study of drugs are as follows:

(1)Affirmation: the use of evidence for the study of drugs, the occurrence of adverse events and research, the use of drugs have a reasonable chronological order, adverse events to study drug interpretation, more reasonable than other explanations. The drug withdrawal reaction is positive, and the repeated use (if feasible) is positive.

⁽²⁾Likely related: evidence of the use of research drugs, occurrence of adverse events, and rational timing of drug use in the study. Adverse events are more reasonable in explaining drug explanations than in other explanations. Positive drug withdrawal reaction.

It may be related to the evidence of the use of research drugs, the occurrence and use of adverse events, and the timing of the study of drugs. Adverse events can also be explained by other reasons. Positive drug withdrawal reaction.

③ Perhaps irrelevant: the use of evidence for the study of drugs, the occurrence of adverse events, explained by other reasons is more reasonable. Withdrawal reactions were negative or unclear. (4) Absolutely unrelated: no use of research drugs, or the use of research drugs and adverse events unrelated to the time, or otherwise clearly lead to adverse events.

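### Two safety rules (important adverse events in Protocol 9.1, one hospitalization exemption in 9.4.3) are reversed as written, and the 9.1 definition of an adverse drug reaction contradicts itself

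*Protocol*

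**What the plan says.** **Important adverse events.** Protocol 9.1 reads: "Important adverse events are any adverse events or laboratory abnormalities that result from the use of targeted medical measures". Its examples of measures are discontinuation, dose reduction and symptomatic treatment, and it sets serious events apart. For the same class, 9.3.1 says that "physicians should promptly inform major researchers, and pause treatment, adjust drug dosage and targeted treatment" follow, according to the subject's condition. The moderate grade in 9.5 adds: "It may interfere with the use of investigational drugs, such as reducing drug dosages or stopping medications".

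**Hospitalization.** Section 9.4.3 opens by making an adverse event serious if it leads to hospitalization or prolongs it. It then gives an exemption: "Hospitalization or prolonged hospital stays unrelated to worsening adverse events are not, in themselves, serious adverse events". One of the examples listed under that exemption is "elective hospitalization with adverse events worsening (e.g., elective cosmetic surgery".

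**Adverse drug reactions.** The first sentence of the definition in 9.1 covers reactions at prescribed doses that are "not as desired, but are causally related to the use of the drug". The second sentence concerns a new drug whose treatment dose is not yet settled, and says that "all harmful reactions that are not expected to cause a causal relationship with the use of the drug should be considered adverse drug reactions". Section 9.6 sets out causality grades and then states: "The first three were considered to be relevant to the study of the drug". Those three (certain, probable, possible) are the ones it evaluates as drug reactions.

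**The concern.** These are working rules that sites apply event by event, and each feeds something downstream.

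- The important class triggers prompt notification of the main researchers under 9.3.1, for inpatients and outpatients. It is also named in 4.5.1 among the grounds on which an investigator may withdraw a subject.
- Seriousness is the gate to the 24-hour report in 9.4.2.
- Adverse reactions are one of the categories that SAP 5(6) compares between the arms.

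If a definition points the wrong way, or in two directions at once, centres can sort the same event differently. In a multicentre trial that means uneven escalation and withdrawal, and in a narrow case a missed expedited report.

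**Working it through.** No arithmetic applies: the point uses no rate, effect size or error level, and the documents give no safety event rates to work from. The check sets each definition beside the other rules that use the same class.

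**1. Important adverse events: direction of cause**

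| Place | Direction |
|---|---|
| 9.1 | measure → event |
| 9.3.1 | event → measure |
| 9.5 (moderate grade) | event → measure |

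As an illustration, take non-serious facial flushing during an infusion (a reaction named in 1.3) for which the infusion is paused. The flushing did not result from the pause, so under the literal 9.1 it is not important. Under 9.3.1 it is the kind of event the class exists for. Conversely, a mild rash caused by a medicine given to treat some other event would be important under 9.1, even if nothing further was done about it. The reversal is therefore complete: 9.1 excludes the events that 9.3.1 acts on and admits others.

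**2. Hospitalization: the item against its own list**

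- The SAE definition in 9.1 counts the need for hospitalization, or its prolongation, as serious.
- The opening sentence of 9.4.3 says the same.
- The stem of the exemption covers only stays unrelated to worsening adverse events.
- The item describes an elective stay with worsening.

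The first three agree, and the item contradicts all of them. Two cases show when this matters. If an elective stay was arranged for another reason and the worsening event neither led to it nor prolonged it, the stem already exempts it and the item changes nothing. If the worsening event led to the stay or prolonged it, the opening sentence makes it serious while the item, read literally, exempts it. Only the second case can lose a 24-hour report, and only when the stay is elective. The example given, cosmetic surgery, suggests that few stays would qualify. Such an event could also still be serious on another criterion in 9.1, such as danger to life or disability.

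**3. Adverse drug reactions: sentence against sentence**

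- First sentence of 9.1: a causal relation is required.
- Section 9.6: the three related grades count. This agrees with the first sentence.
- Second sentence of 9.1: reactions not expected to be causal count. This disagrees with both.

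The second sentence applies only while the dose is undetermined. Section 6.1.4 fixes 20 mg once a day for two days, which points to the sentence not applying. On the other side, the uses listed in 1.2 do not include spontaneous intracerebral hemorrhage, so a site might think that the trial falls within the new-drug condition. The documents do not settle this. If the sentence did apply, a reaction judged unrelated would be a drug reaction under 9.1 and not under 9.6.

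**4. What reaches the SAP**

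SAP 5(6) names complications, adverse events and adverse reactions. Only item 3 concerns a category named there. Items 1 and 2 act through handling, withdrawal and reporting.

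**The case against.** The strongest reply is that these are translation slips with an obvious intent. The English is rough throughout, the documents include no source-language text, and it is not shown that sites worked from this wording. Section 9.3.1 uses the important class in the intended direction, and a physician who has recognised an event as important will notify the main researchers however 9.1 is phrased. An item under a stem cannot sensibly extend that stem to its opposite. The drug reaction definition starts with a sound sentence, its faulty sentence is conditional, and 9.6 supplies the working rule.

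Much of this stands. The intent can be inferred, and that is why the repair is easy. But this is the text as given, and 9.3.1 helps only after an event has been recognised as important, which is the step that 9.1 is meant to govern.

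Some stronger readings are tempting, and the documents do not support them:

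- *That the adverse reaction rate could rise to nearly all adverse events.* This needs the first sentence of the definition, the condition on the second sentence and 9.6 all to be set aside.
- *That events would in general go unreported.* Section 9.3.2 requires adverse events to be recorded with no limit by class, and 9.4.2 covers serious events whether or not they are related to the drug. Only the 9.4.3 item could cost a report, and then only the expedited one.
- *That the SAP compares the arms on important or serious events.* SAP 5(6) names neither class. It also lists each adverse event in detail, so a misclassed event stays visible.

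**Conclusion.** The point holds in limited form. The important adverse event definition in 9.1 is fully reversed against 9.3.1 and 9.5. One item in 9.4.3 is reversed against its own stem, the opening sentence of that section and the SAE definition in 9.1. The adverse drug reaction definition is not inverted as a whole: one conditional sentence contradicts the rest.

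No numerical size can be given. For important events, the effect falls on escalation and investigator-decided withdrawal. For the hospitalization item, it is a possible missed 24-hour report in a small set of elective stays. For drug reactions, it is an ambiguity in one planned safety comparison, and it matters only if the conditional sentence is taken to apply. No efficacy result is affected.

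This rests on two assumptions: that the English text is what sites and safety staff apply, and that 9.3.1, 9.5, 9.6 and the stem of 9.4.3 express the intended direction. The correction should be made because it costs little and concerns safety classification, but the trial's conclusions do not turn on it.

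**What to change.** Make three wording corrections, each of which only aligns a definition with other text in the protocol:

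1. In 9.1, define important adverse events as those that *lead to* targeted medical measures, in agreement with 9.3.1 and 9.5.
2. In 9.4.3, change *with* to *without* in the elective hospitalization item, so that it agrees with its stem.
3. In 9.1, remove the second sentence of the adverse drug reaction definition, or align it with the related grades in 9.6.

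Carry the same wording into the case report form guidance. If events have already been classified, check important events, elective stays and drug reactions against the corrected text. None of this sets a dose or a rule for pausing or stopping treatment. The cost is a short protocol amendment and a note to sites, with no new data collection and no change to the SAP analyses.
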